#### **7.4.5 Adjustment for Covariates**

Baseline (pre-dose) measurement will be included as a covariate, where applicable, in the mixed effects models.

#### **7.4.6 Adjustment for Multiple Comparison/Multiplicity**

No adjustments will be made for multiple comparisons. The primary hypotheses follow a hierarchical (sequential) testing method, and all doses of GE-IR should show statistical significance in the hypothesis testing.

## 8. PHARMACOKINETICS ANALYSIS

---

### 8.1 Pharmacokinetic Analysis

The PK analysis will be carried out according to Altasciences standard operating procedures (SOPs).

#### 8.1.1 Concentration Data

Plasma concentrations of gabapentin resulting from the single 200 mg, 450 mg, and 700 mg dose administration of the investigational product (GE-IR) from the treatment phase will be determined to establish the PK profile of gabapentin in healthy, nondependent, recreational drug users with sedative experience.

#### 8.1.2 Missing Values

The lack of concentration values due to failure to collect the sample, a lost or compromised sample or due to the subject's early termination from the study will be termed "missing" in the dataset, and no imputation will be done.

If the actual collection time of a postdose PK sample is unknown, but a valid concentration value has been measured, the sample will be set to missing in the PK analysis and descriptive statistics, but the concentration value will be presented in the concentration listing. Unknown baseline collection times will be handled on a case-by-case basis.

#### 8.1.3 Measurements Below the Lower Limit of Quantitation

Concentration values below the lower limit of quantitation (LLOQ) associated with predose and postdose collection times will be replaced with zero for the non-compartmental analyses (NCA).

Concentration values below the LLOQ will be replaced with zero for mean PK profile representations as well as for descriptive statistic calculations.

#### 8.1.4 Actual Times

The NCA will be based on the actual sampling times, except for predose samples, which will always be reported as zero, regardless of time deviations.

The individual concentration/time profiles will be presented using actual sampling times whereas the mean concentration/time profiles and tables presenting summary statistics of concentration-time series will be presented using nominal sampling times. Concentration profiles will be presented on both linear and semi-logarithmic scales.

Individual actual times will be listed.

#### 8.1.5 Non-Compartmental Analysis

The PK analyses will be based on the PK population.

The following configuration for the NCA (with Phoenix® WinNonlin® version 8, or higher) will be used:

Reason for exclusion of AUC: In the case where less than 3 consecutive measurable concentrations are observed, the AUC parameters will not be estimated.

The PK parameters to be determined are defined in Table 5.

Table 5: Pharmacokinetic Parameters in Plasma

PK Parameter	Definition
$C_{\max}$ (ng/mL)	Maximum observed concentration occurring at time $T_{\max}$
$T_{\max}$ (h)	Time of maximum observed concentration. If the maximum observed concentration is not unique, then the first maximum is used.
$AUC_{0-1}$ (h*ng/mL),	Area under the concentration-time curve from the time 0 to 1 h
$AUC_{0-2}$ (h*ng/mL),	Area under the concentration-time curve from the time 0 to 2 h
$AUC_{0-12}$ (h*ng/mL),	Area under the concentration-time curve from the time 0 to 12 h
$AUC_{0-24}$ (h*ng/mL),	Area under the concentration-time curve from the time 0 to 24 h
$AUC_{0-T}$ (h*ng/mL),	Area under the concentration-time curve from the time 0 to $T_{\text{last}}$
$AUC_{0-\infty}$ (h*ng/mL),	Area under the concentration-time curve from the time 0 extrapolated to infinity
$T_{1/2}$ (h)	Terminal elimination half-life
$T_{\text{last}}$ (h)	Time of last measurable (positive) observed concentration
$\lambda_z$ (1/h)	Individual estimate of the terminal elimination rate constant, calculated using log-linear regression of the terminal portions of the plasma concentration-versus-time curves

### 8.1.6 Summary Statistics

Summary statistics of the individual concentration data and derived parameters will be calculated with Phoenix® WinNonlin® for the PK population. Summary statistics will be calculated for concentrations at each individual time point and for all PK parameters.

Concentration data will be summarized by group using the following statistics: number of observations (N), mean, SD, minimum (min), median, maximum (max), and coefficient of variation percentage (CV%). Pharmacokinetic parameters will be summarized using these same statistics, as well as geometric mean and geometric mean CV%.

Summary statistics will be displayed with the same precision as the individual values (Section 10.2) with the exception of N and CV% which will be presented with 0 and 1 decimal place, respectively; SD and CV% will not be calculated when N<3, and only min and max will be reported if N=1.

## **9. SAFETY**

---

For the treatment phase, the following safety endpoints will be evaluated: incidence, maximum severity and maximum relationship of AEs, AEs leading to discontinuation and SAEs, clinical laboratory assessments (hematology, biochemistry, urinalysis), vital signs [e.g. systolic and diastolic blood pressure, pulse rate, respiratory rate, oral temperature, SpO2], continuous SpO2 monitoring, continuous EtCO2 monitoring, ECGs, physical examination findings, and Columbia-Suicide Severity Rating Scale (C-SSRS). All safety analyses will be conducted on the Safety population. By-subject listings of adverse events will be based on the Qualification Safety population if occurring in the qualification phase and the Safety population if occurring in the treatment phase. All other listings for safety endpoints will be based on the Qualification Randomized population.

### **9.1 Adverse Events**

#### **9.1.1 Qualification Phase**

The Qualification Safety population will be used to list all AEs occurring in the Qualification phase. Qualification passes and failures will be listed separately.

## 9.1.2 Treatment Phase

An AE is defined as any untoward medical occurrence in a clinical investigation subject administered an investigational product and which does not necessarily have a causal relationship with the treatment. An AE can therefore be any unfavorable and unintended sign (including a clinically significant abnormal laboratory finding, for example), symptom, or disease temporally associated with the use of an investigational product, whether or not related to the investigational product.

Treatment emergent adverse events (TEAEs) are AEs not present prior to the exposure to study treatment or AEs already present that worsen in intensity or frequency following exposure to study treatment.

All TEAEs will be assigned to a treatment using the following rules:

- A TEAE will be assigned to the last treatment taken by the subject where the date and time of the last treatment dosing is on or before of the start date and time of the event. Such assignment will be performed irrespective of any washout period between the start and stop dates of the TEAE.
- Any TEAE started during the follow-up period will be assigned to the last treatment that the subject has taken.

### 9.1.2.1 Severity Categorization

The severity of AEs must be recorded during the course of the event, including the start and stop dates for each change in severity. An event that changes in severity should be captured as a new event. Worsening of pre-treatment events, after initiation of the study drug, must be recorded as new AEs on the appropriate electronic case report form (eCRF) page.

The medical assessment of severity is determined by using the following definitions:

Term	Severity Definition
Mild:	Causing no limitation of usual activities; the subject may experience transient slight discomfort.
Moderate:	Causing some limitation of usual activities; the subject may experience annoying discomfort.
Severe:	Causing inability to carry out usual activities; the subject may experience intolerable discomfort or pain.

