6.1.4 Vital Signs

Vital signs will be measured as scheduled in [Table 1](#) and will include blood pressure, pulse rate, respiratory rate and SpO₂ measures at designated times.

All vital signs will be interpreted by an investigator as normal, abnormal not clinically significant (NCS), or abnormal clinically significant (CS). New or worsening abnormalities that are judged to be clinically significant will be recorded as AEs.

Vital signs will be measured after being in supine or semi-supine position for at least 5 minutes.

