### **9.1.2.4 Summaries of Treatment-Emergent Adverse Events**

- Summary of TEAEs by System Organ Class (SOC), Preferred Term (PT), and Treatment
  - A summary of the number and percentages of subjects who experienced at least one TEAE, and the number and percentages of subjects who experienced each SOC and each PT within each SOC will be presented by treatment and overall. In addition, the number of events will be summarized for each of these categories.
- Summary of TEAEs by SOC, PT, Treatment and Maximum Severity
  - A summary of the number and percentages of subjects who experienced at least one TEAE by maximum severity as well as the number and percentages of subjects who experienced each SOC and each PT within each SOC by maximum severity will be presented by treatment. For this analysis, if a subject has more than one occurrence of the same PT, then the PT will be counted only once for that subject under the maximum severity at which it was experienced (mild, moderate or severe).

- Summary of TEAEs by SOC, PT, Treatment and Maximum Relationship
  - A summary of the number and percentages of subjects who experienced at least one TEAE by maximum relationship as well as the number and percentages of subjects who experienced each SOC and each PT within each SOC by maximum relationship will be presented by treatment. For this analysis, if a subject has more than one occurrence of the same PT, then the PT will be counted only once for that subject under the maximum relationship at which it was experienced (reasonable possibility or no reasonable possibility).

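### Every change in AE severity, including improvement, opens a new event, and the event counts by treatment have no rule to bring one episode's records back together

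*SAP*

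**What the plan says.** SAP 9.1.2.1 (Severity Categorization) has three relevant sentences.

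- On recording: "The severity of AEs must be recorded during the course of the event, including the start and stop dates for each change in severity". This describes one event with several dated grades.
- The next sentence goes further: "An event that changes in severity should be captured as a new event". It does not distinguish worsening from improvement.
- The third is limited to worsening, but only for conditions that predate treatment: "Worsening of pre-treatment events, after initiation of the study drug, must be recorded as new AEs".

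SAP 9.1.2 (Treatment Phase) defines TEAEs as "AEs not present prior to the exposure to study treatment or AEs already present that worsen in intensity or frequency following exposure to study treatment". It then sets the attribution rule: "A TEAE will be assigned to the last treatment taken by the subject where the date and time of the last treatment dosing is on". Dosing time is compared with the event's start time, earlier dosing included, and any washout in between is disregarded.

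Event numbers are reported in two places. Each row of the overall TEAE table in SAP 9.1.2.3 gives an event count beside the subject count. For the SOC/PT table, SAP 9.1.2.4 adds: "In addition, the number of events will be summarized for each of these categories". The rule in 9.1.2.4 that counts a preferred term once per subject belongs to the maximum-severity and maximum-relationship tables and governs subjects. Nothing comparable is stated for events.

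Protocol 7.2 and 7.4 contain no instruction to open a new record at a grade change, and SAP section 12 does not list one among its changes to the protocol.

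**The concern.** Splitting a record at each grade change is harmless if the pieces are rejoined before events are counted. The SAP does not say that they are. Read literally, an episode that builds up and wears off contributes more events than one that stays mild throughout, even though each is one episode in one subject.

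That matters here because the secondary safety objective sets GE-IR beside alprazolam and placebo. Protocol 1.2 names sedation, somnolence and dizziness as the most commonly reported AEs with Horizant. Effects of this kind can rise and fall within a dosing period. Someone comparing event counts across the five treatments would read differences in the shape of an effect as differences in how often it occurred.

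A second, smaller question concerns attribution. A record opened on improvement has its own start time, and attribution follows the start time. If the improvement comes after the next dose, the SAP does not make clear whether the record belongs to the next treatment or is not a TEAE of that treatment at all.

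**Working it through.** The plan gives no figure on this point, so there is none to reproduce. The check applies the stated rules to example cases.

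**Step 1: records per episode.** Under SAP 9.1.2.1 as written, records = 1 + number of grade changes in either direction. Two alternatives are shown for comparison.

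| Severity course | Any change (as written) | Worsening only | One event at maximum severity |
|---|---|---|---|
| mild | 1 | 1 | 1 |
| moderate-mild | 2 | 1 | 1 |
| mild-moderate-mild | 3 | 2 | 1 |
| severe-moderate-mild | 3 | 1 | 1 |
| mild-moderate-severe-moderate-mild | 5 | 3 | 1 |

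Limiting the rule to worsening would not be enough by itself: mild-moderate-mild would still count as 2.

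**Step 2: effect on a table cell.** Assume 24 affected subjects on one treatment, one episode each. A share *q* follow mild-moderate-mild and the rest stay at one grade. Neither 24 nor *q* comes from the documents, so the whole range of *q* is shown.

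Events = 24 × (1 − *q*) + 24 × *q* × 3

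- *q* = 0%: 24 + 0 = 24
- *q* = 25%: 18 + 18 = 36
- *q* = 50%: 12 + 36 = 48
- *q* = 100%: 0 + 72 = 72

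The subject count is 24 in every case.

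**Step 3: when a record can move to another treatment.** Doses are at least 3 days apart (SAP 3.1), about 72 h. A grade change before the next dose stays with the treatment already assigned. Only a later change can move, and after the fifth dose there is no next treatment.

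Protocol 1.2 gives a gabapentin half-life of 4.38 to 5.47 h after GE-IR and says that alprazolam effects are back to baseline by 24 h. The documents give no distribution of the time to a step down in grade. If it were exponential with mean *m* hours (assumed), the share beyond 72 h would be exp(−72/*m*):

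- *m* = 12: 0.2%
- *m* = 24: 5%
- *m* = 48: 22%
- *m* = 72: 37%

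The longer means are hard to reconcile with the stated half-life and duration of effect, so movement should be uncommon for drug-related AEs.

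**Step 4: whether a moved record is a TEAE.** For an AE that is not new, the definition requires worsening: "AEs already present that worsen in intensity or frequency following exposure to study treatment". If exposure means the dose of each period, an AE that started earlier and eases after a later dose was already present and has not worsened, so it is not a TEAE of the later treatment. If exposure means the first dose, the record opened on easing is a new event that was absent before exposure, so it qualifies and goes to the later treatment. The SAP does not say which is meant. On the first-dose reading, the moved record would also add a subject to the later treatment's count if that subject had no other such event there.

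**The case against.** The strongest reply is that the outputs that matter are not touched. Protocol 8.7.3.2 bases the safety summaries on numbers and percentages of subjects. SAP section 9 names incidence, maximum severity and maximum relationship. All percentages use subjects, and the severity and relationship tables count a preferred term once per subject. Splitting within a treatment alters none of this. Event numbers are supplementary, and no event rate, event ratio or test on AEs is planned. All of that stands, and it limits the point to the event-count columns.

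A second reply is that the sentence is a data-capture convention, placed beside an instruction about the eCRF. That is a fair reading of its purpose. It does not close the gap, because no later section says how captured records become counted events.

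Third, a reader might infer that the protocol is contradicted, since Protocol 6.1.4 says "New or worsening abnormalities that are judged to be clinically significant will be recorded as AEs". The documents do not support that. The sentence decides which vital-sign findings become AEs, not how grade changes within an existing AE are recorded. Protocol 7.2 is silent on that, so the SAP adds detail to the protocol without conflicting with it.

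Fourth, a reader might infer that a resolving AE is generally charged to the next treatment. The documents do not support that either. It needs a grade change after the next dose, at least 3 days on, and also the first-dose reading of exposure.

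Finally, the size is unknown. The documents give no frequency of grade changes, and Protocol 1.4.1 describes the AEs in the multiple ascending dose study of GE-IR as mild, which suggests few transitions on the test drug. This is why a range is shown and no single inflation factor is claimed.

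**Conclusion.** The point holds for event counts. As written, the SAP counts one AE episode once per severity state, 3 for mild-moderate-mild and 5 for mild-moderate-severe-moderate-mild, and has no rule to undo this in SAP 9.1.2.3 or 9.1.2.4. For 24 affected subjects the reported number could lie anywhere from 24 to 72, depending on the share who follow mild-moderate-mild. The records per episode follow directly from the rule; the 24 subjects and the shares are assumptions.

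It does not hold for subject counts and percentages within a treatment, which are the protocol's basis for the safety summaries, and it does not touch the primary endpoint. Assignment of an easing AE to a later treatment is possible but uncommon, and depends on an ambiguity in the TEAE definition. It is a reason to clarify that definition, not a separate finding of misattribution. The change should be made because the plan states a rule that gives misleading reported numbers and the correction is small.

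**What to change.** Revise SAP 9.1.2 to 9.1.2.4 as follows.

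1. Keep the dates of severity changes, but as linked rows under one event identifier.
2. In every event-count column of 9.1.2.3 and 9.1.2.4, count the linked rows as one event, at maximum severity, under the treatment at first onset.
3. Count a new TEAE under a later treatment only if the condition worsens after that later dose.
4. State that exposure in the TEAE definition is judged per treatment period.
5. Keep the exception in Protocol 7.6: a non-serious AE that worsens and becomes serious is still recorded as a new SAE.

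If the sponsor already intends to collapse the records, a sentence saying so would settle the counting part; the meaning of exposure would still need to be stated. The cost is SAP wording, a linking identifier in the AE dataset and minor programming. No further data or visits are needed.

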### 9.1.2.2 Relationship Categorization

The causality assessment must be documented in the source document and the AE will should be considered as “reasonable possibility” and “not reasonable possibility”.

The following additional guidance may be helpful:

Term	Relationship Definition
Reasonable Possibility	A temporal relationship exists between the AE onset and administration of the investigational product that cannot be readily explained by the subject's clinical state or concomitant therapies. Furthermore, the AE appears with some degree of certainty to be related,

Term	Relationship Definition
	
based on the known therapeutic and pharmacologic actions or AE profile of the investigational product.
 
In case of cessation or reduction of the dose the AE may abate or resolve and it may reappear upon rechallenge.

No Reasonable Possibility	
Evidence exists that the AE has an etiology other than the investigational product.
 
For SAEs, an alternative causality must be provided (e.g., preexisting condition, underlying disease, intercurrent illness, or concomitant medication).

### **9.1.2.3 General Summary of Treatment-Emergent Adverse Events**

An overall summary table of all TEAEs by treatment at onset and overall for the treatment phase will be produced to present data below:

- Number and percentages of subjects (number of events) with any TEAE
- Number and percentages of subjects (number of events) with study drug discontinued due to TEAE
- Number and percentages of subjects (number of events) with severe TEAE
- Number and percentages of subjects (number of events) with any related TEAE
- Number and percentages of subjects (number of events) with any serious TEAE
- Number and percentages of subjects (number of events) with any serious TEAE leading to death

The denominator for percentages will be the total number of subjects in the Safety population by treatment and overall.

### **9.1.2.4 Summaries of Treatment-Emergent Adverse Events**

- Summary of TEAEs by System Organ Class (SOC), Preferred Term (PT), and Treatment
  - A summary of the number and percentages of subjects who experienced at least one TEAE, and the number and percentages of subjects who experienced each SOC and each PT within each SOC will be presented by treatment and overall. In addition, the number of events will be summarized for each of these categories.
- Summary of TEAEs by SOC, PT, Treatment and Maximum Severity
  - A summary of the number and percentages of subjects who experienced at least one TEAE by maximum severity as well as the number and percentages of subjects who experienced each SOC and each PT within each SOC by maximum severity will be presented by treatment. For this analysis, if a subject has more than one occurrence of the same PT, then the PT will be counted only once for that subject under the maximum severity at which it was experienced (mild, moderate or severe).

- Summary of TEAEs by SOC, PT, Treatment and Maximum Relationship
  - A summary of the number and percentages of subjects who experienced at least one TEAE by maximum relationship as well as the number and percentages of subjects who experienced each SOC and each PT within each SOC by maximum relationship will be presented by treatment. For this analysis, if a subject has more than one occurrence of the same PT, then the PT will be counted only once for that subject under the maximum relationship at which it was experienced (reasonable possibility or no reasonable possibility).

## 9.2 Clinical Laboratory Evaluations

General biochemistry, hematology, and urinalysis assessments, and other laboratory tests are listed in Table 6.

Table 6: Clinical Laboratory Assessments

Clinical Laboratory Test Panel	Description
General biochemistry:	Sodium, potassium, chloride, glucose, blood urea nitrogen (BUN), creatinine, bilirubin total, alkaline phosphatase, aspartate aminotransferase (AST), alanine aminotransferase (ALT), and albumin
Endocrinology:	Follicle stimulating hormone (FSH; for female subjects)
Hematology:	White cell count with differential (absolute values of neutrophil, lymphocyte, monocyte, eosinophil, and basophil), red cell count, hemoglobin, hematocrit, mean corpuscular volume (MCV), and platelet count
Serology*	Human immunodeficiency virus (HIV) antigen/antibody (Ag/Ab) Combo, Hepatitis B (HBsAg (B)) and Hepatitis C (HCV (C))
Urinalysis:	Color, clarity, specific gravity, pH, leukocyte, protein, glucose, ketones, bilirubin, blood, nitrite, urobilinogen. Microscopic examination will only be performed if the dipstick test is outside of the reference range for leukocyte, blood, nitrite or protein
Urine drug screen (UDS)	Alcohol, amphetamines, barbiturates, cannabinoids, cocaine, opiates, benzodiazepines, and phencyclidine
Urine OR serum pregnancy test:	To be performed for all female subjects

\*Serology will be done at screening only.

Laboratory data collected during the treatment phase will be summarized by the type of laboratory test and visit. Descriptive statistics (n, mean, SD, minimum, median, and maximum), and the number of subjects with laboratory test results below, within, and above normal ranges will be tabulated by laboratory test and visit.

All laboratory data will be listed by laboratory panel and test. Laboratory abnormalities and clinically significant abnormalities during the treatment phase will also be listed.

